The secondary endpoints include:

- Rates of achieving a critical view of safety.
- Rates of different bailout procedures initiated when safe cholecystectomy is compromised.
- 30-day and one-year rates of textbook outcomes [2] for cholecystectomy, which covers: postoperative complications (Clavien-Dindo classification), intraoperative complications (including bile duct and vascular injuries), length of stay, readmission, mortality, and postoperative imaging or intervention.
- Unsuspected gallbladder cancer rates and their 30-day and one-year outcome rates, which includes: (1) complication rates (Clavien-Dindo classification); (2) time-to-recurrence rates (time from surgery to recurrence); and (2) revisional surgery rates (liver resection, bile duct resection and/or lymph node dissection).
- A description of the global variation in the availability of cholecystectomy services, training and sustainable practice.

Control of Bias and Confounding

Data will be collected on audit standards and confounding factors for risk-adjusted analyses. These include age, sex, body mass index, American Society of Anaesthesiologists (ASA) grade, and relevant comorbidities. Variables including operative urgency, operative contamination, and operative approach will also be collected. Without appropriately adjusting for risk factors, it is likely that any findings would be biased and unable to be appropriately analysed on an international scale. A full list of required data fields is available in **Appendix B**, and on the REDCap database.

Data Analysis & Sample Size

Variation across different international health settings will be tested using the human development index (HDI) countries [17] a composite statistic of life expectancy, education and income indices published by the United Nations. Initially, data will be reported using descriptive analyses. Comparisons between groups will be undertaken using appropriate parametric and non-parametric analyses. Multilevel logistic regression multivariate models will be constructed to account for case mix, with population stratification by hospital and country as random effects.

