Discussed at MDT	 Yes  No	Adjuvant treatment  Chemotherapy  Radiotherapy  None	
Revisional surgery	 Yes  No - not required  No - unresectable tumour		
Type of revisional surgery (Tick all that apply)	 Liver resection (Extent:  Liver bed  1 segment  2 segments  ≥ 3 segments)  Bile duct resection  Lymph node dissection	Days from histology result to revisional surgery --	If revisional surgery
Pathology results	Resection margin status:  R0  R1  R2 Lymphovascular invasion:  Yes  No Perineural invasion:  Yes  No		
Recurrence on imaging at one year	 Yes (Days from surgery to recurrence: __)  No		
Section 6: One-year outcomes			
Highest one-year Clavien-Dindo (CD)	 0  I  II  IIIa (Radiological drainage?  Yes  No)  IIIb (Re-operation?  Yes  No)  IVa  IVb  V (Postop day of death: __)	Total number of readmissions --	

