APPENDIX B: DATA DICTIONARY

Pre-operative Data Fields	Required data (definition / comment)
1. Patient age	Years (Whole years at the time of operation)
2. Patient sex at birth	Male / Female
3. ASA grade	I / II / III / IV / V (Appendix D for definitions)
4. Body Mass Index (BMI in kg/m ²)	Underweight BMI Below 18.5 / Normal weight BMI 18.5-24.9 / Pre-obesity BMI 25.0-29.9 / Obesity class I BMI 30.0-34.9 / Obesity class II BMI 35.0-39.9 / Obesity class III BMI 40+
5. Clinical Frailty Scale	1 / 2 / 3 / 4 / 5 / 6 / 7 / 8 / 9 (Appendix D for definitions)
6. Comorbidities (Select all that apply)	
Myocardial Infraction (MI) / Congestive Heart Failure (CHF) / Peripheral Vascular Disease (PVD) Cerebrovascular Accident (CVA) or Transient Ischaemic Attack (TIA) / Dementia / Chronic Obstructive Pulmonary Disease (COPD) / Connective Tissue Disease (CTD) Peptic Ulcer Disease (PUD) / Hemiplegia / Leukaemia / Lymphoma / Human Immunodeficiency Virus (HIV) or Acquired Immunodeficiency Syndrome (AIDS) / Hypertension / Inflammatory Bowel Disease (IBD) / Diabetes Mellitus (Type 1 or Type 2). If yes: Diet-Controlled / Medication (non-insulin) controlled / Insulin-controlled Solid Tumour. If yes: Localised / Metastatic Liver Disease. If yes: Mild / Moderate to Severe Chronic Kidney Disease (CKD). If yes: Stage I / II / IIIa / IIIb / IV / V None of the Above
 
Definitions:
 
 eGFR for CKD stages: I ≥ 90; II = 60-90; IIIa = 45-59; IIIb = 30-44; IV = 15-29; V <15 Definitions for Liver Disease: Mild defined as chronic hepatitis or cirrhosis without portal hypertension; Moderate defined as cirrhosis and portal hypertension but no variceal bleeding history; Severe defined as cirrhosis and portal hypertension with variceal bleeding history.
7. History of acute cholecystitis or cholangitis	Yes / No
8. Number of admissions with biliary symptoms in previous 12 months prior to surgery	Number of admissions excluding the current one
9. Preoperative imaging (Select all that apply)	Yes / Unknown / No (Not available / Not indicated / Patient declined) for each of the following: USS / CT / ERCP / MRCP / Endoscopic Ultrasound (EUS) / Hepatobiliary IminoDiacetic Acid (HIDA)

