
6. Imaging modality to investigate and confirm BDI
	
On-table cholangiography (OTC) / USS / MRCP / CT / ERCP / Percutaneous transhepatic cholangiography (PTC) / Nuclear medicine scan (e.g. Functional liver scan) / Tubogram / None

7. Discussion with a specialist HPB centre
	
Yes / No / Not required (Injury occurred at specialist HPB centre) If yes:
 
 Transferred to specialist HPB centre: Yes / No Time from injury to referral: number of days (whole number)

8. Management of Bile duct injury (Select all that apply)
	
Non-surgery (ERCP only / ERCP and stent / PTC) / Surgery (washout only / repair) If any of the above:
 
 Time after index cholecystectomy: number of days (Whole number, day of index cholecystectomy = day 0) 
If surgical repair:
 
 Specialty of surgeon performing Bile duct injury repair: HPB surgeon / UGI surgeon / General surgeon Method of repair: Roux-en-Y Hepaticojejunostomy / CBD repair without T-tube / CBD repair with T-tube / CBD end to end anastomosis / Hepaticoduodenostomy Vascular repair: Yes / No One-year complications: Stricture formation / Cholangitis / anastomotic leakage / intra-abdominal abscess or biloma / re-repair. If yes to any, time from repair to complication: number of days (Whole number, day of repair = day 0)

	Stricture definition: defined as a clinically relevant stricture leading to either jaundice, significant alterations of the liver function tests, cirrhosis or reoccurring cholangitis requiring radiological/surgical intervention or a liver failure related death
Histology data fields	Required data (definition / comment)
1. Postoperative histology	
Not sent for examination / Sent for examination
 
If sent for examination, please complete:
 
 • Indication: Routine / Selective • Time from index cholecystectomy to histology result: Number of days (whole number) • Result: Benign / Malignant 
If Malignant, please complete the rest of the data points below

2. Staging investigations after index cholecystectomy (select all that apply)	
CT thorax abdomen pelvis / MRI liver / PET-CT / Staging laparoscopy
 
For any of the above, please indicate time from histology result to staging investigation: number of days (whole number)

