3. TNM grade (AJCC 8th edition) (Appendix D for definition)	
T category: Tis / T1a (lamina propria) / T1b (muscularis) / T2a (peritoneal side) / T2b (hepatic side) / T3 / T4
 
N category: N0 / N1 (1-3 nodes) / N2 (>3 nodes)
 
M category: M0 / M1

4. Discussed at MDT	Yes / No
5. Adjuvant treatment	No / Chemotherapy / Radiotherapy
6. Revisional surgery completed	
Yes / No (not required) / No (unresectable tumour)
 
 • If yes, type of surgery (select all that apply): Liver resection (liver bed / one segment / two segments/ ≥ 3 segments) / bile duct resection / lymph node dissection • If yes, time from histology result to revisional surgery: Number of days (whole number)
7. Pathology results if revisional surgery	
Resection margin status: R0 / R1 / R2
 
Lymphovascular invasion: Yes / No
 
Perineural invasion: Yes / No
 
Resection margin definition: R0 = microscopically negative for residual tumor; R1 = microscopically margins still demonstrate the presence of tumor; R2 = macroscopically-visible disease remains post-surgery.

8. Recurrence on imaging at one year	
Yes / No
 
If yes, time from surgery to recurrence: number of days (whole number)

One-year Outcomes	Required data (definition / comment)
1. Highest one-year Clavien-Dindo (CD) Grade	
0 / I / II / IIIa / IIIb / IVa / IVb / V
 
If CD IIIa: Radiological drainage (yes / No)
 
If CD IV: Re-laparoscopy (yes / No)
 
If CD V (death): please indicate time from index cholecystectomy to death: number of days (whole number)

2. Readmissions	Total number of readmissions

3. One-year complications
(Select all that apply)

Surgical site infection (CD Grade* 0 / I / II / IIIa / IIIb / IVa / IVb / V)

Postoperative pulmonary complications (CD Grade* 0 / I / II / IIIa / IIIb / IVa / IVb / V)

Bile leak (CD Grade* 0 / I / II / IIIa / IIIb / IVa / IVb / V)

Biliary stricture (CD Grade* 0 / I / II / IIIa / IIIb / IVa / IVb / V)

Bleeding (CD Grade* 0 / I / II / IIIa / IIIb / IVa / IVb / V)

Intra-abdominal collection (CD Grade* 0 / I / II / IIIa / IIIb / IVa / IVb / V)

Acute pancreatitis (CD Grade* 0 / I / II / IIIa / IIIb / IVa / IVb / V)

*For all of the above, please indicate the Clavien-Dindo grade associated with that complication

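### The cancer section has no code for revisional surgery that was indicated but not done, or for patients who were never disease-free or never imaged

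*Protocol*

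**What the plan says.** Secondary aim 3 of the protocol is the rates and outcomes of unsuspected gallbladder cancer. Under Secondary Outcome Measures, the cancer endpoint includes "time-to-recurrence rates (time from surgery to recurrence") and "revisional surgery rates (liver resection, bile duct resection and/or lymph node dissection").

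The data for these come from the histology section of Appendix B and from Section 5 of the case report form (Appendix A):

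- **Who completes the section.** Once the histology result is malignant, the instruction is "please complete the rest of the data points below".
- **Field 6, revisional surgery.** The options are "Yes / No (not required) / No (unresectable tumour". The case report form has the same two reasons for No, the second being "No - unresectable tumour".
- **Field 7, margin and invasion status.** This carries its own condition: "Pathology results if revisional surgery".
- **Field 8.** "8. Recurrence on imaging at one year" is answered Yes or No. A number of days from surgery is requested only if the answer is Yes.

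Elsewhere the same dictionary is fuller. Preoperative imaging is recorded as "Yes / Unknown / No (Not available / Not indicated / Patient declined) for each of the following", and the bile duct injury section keeps a plain No apart from Not required when it asks about discussion with a specialist centre.

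**The concern.** Field 6 assumes that a patient who was not re-operated either did not need it or could not be resected. In a worldwide cohort that is open to any hospital, other reasons are foreseeable: refusal, unfitness, no access to the service, death before surgery, or surgery still pending at one year. None has a true code.

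Field 8 assumes that every patient with cancer became disease-free and was imaged. The form itself allows for M1 disease, unresectable tumour and R2 margins, so some patients will have persistent disease rather than recurrence. Follow-up is by each hospital's routine practice, so some will have had no imaging. A bare Yes/No merges all of these with true recurrence or true freedom from it.

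Two named components of a secondary endpoint depend on these fields. The revision rate becomes harder to interpret, and the recurrence measures may be wrong.

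**Working it through.** The protocol gives no expected cancer or recurrence figure, so there is nothing of its own to reproduce. The check compares the fields and then bounds the size of the problem under stated assumptions.

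**1. Is the option missing in both places?** Yes. The dictionary and the case report form agree on one Yes and two reasons for No, so this is not an extraction fault.

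**2. Is recurrence asked of every malignant case?** The dictionary says so. Field 7 is conditional on revisional surgery; field 8 has no condition, and the instruction after a malignant result covers all later fields. In the case report form the table layout is broken near these rows, so it neither confirms nor contradicts this.

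**3. Can a blank serve as the missing code?** Poorly. Study Setting excludes centres with more than 10% missing data, and Authorship requires more than 95% of data points per record. Both discourage blanks, and a blank gives no reason.

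**4. How many patients?** Assumption: unsuspected cancer in 0.2% to 1% of the anticipated 15,000.

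- 15,000 × 0.002 = 30
- 15,000 × 0.01 = 150

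Assumption: 10% to 30% of these needed re-resection and did not get it for an unlisted reason.

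- 30 × 0.10 = 3
- 150 × 0.30 = 45

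So roughly 3 to 45 patients would be miscoded or left blank in field 6.

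**5. Is the crude revision rate affected?** No. Take an assumed 60 cancers with 25 re-operated: Yes over malignant is 25/60 = 42%, however the other 35 are coded. Only the breakdown of those 35 is affected.

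**6. How far can crude recurrence move?** Let u be the share of malignant cases never disease-free, and r the recurrence proportion among the disease-free.

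- All never-disease-free patients ticked No: (1 − u) × r
- All ticked Yes: u + (1 − u) × r
- Difference between the two: u

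| u (assumed) | r (assumed) | all ticked No | all ticked Yes |
|---|---|---|---|
| 0.1 | 20% | 18% | 28% |
| 0.3 | 20% | 14% | 44% |
| 0.5 | 20% | 10% | 60% |
| 0.1 | 40% | 36% | 46% |
| 0.3 | 40% | 28% | 58% |
| 0.5 | 40% | 20% | 70% |

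The first coding understates r and the second overstates it. The dictionary does not say which to use. If never-disease-free patients had their own code, the proportion among the rest would return r and the gap of u would fall to 0.

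**7. Time to recurrence.** Time is recorded only for Yes, and no last-imaging date is collected for No. Day of death is available through Clavien-Dindo grade V. For a surviving patient ticked No, nothing shows when they were last known to be disease-free. Censoring them all at one year would assume imaging that may not have been done.

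**8. Can the analysis repair it?** In part. M1, unresectable and R2 cases are coded and can be excluded. Three groups remain: M0 patients who were not revised, whose margin status is never collected; patients miscoded in field 6; and patients who were not imaged.

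**The case against.** The strongest reply is that the protocol does not set out to measure unmet need. Aim 3 is rates and outcomes, the endpoint is a revision rate, and that rate is recorded correctly. This stands.

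A reader might infer that aim 3 will show no unmet need, or that delivery of indicated surgery will read 100% everywhere. In the example of 60 cancers, suppose 32 were indicated and resectable and 25 of them were operated on. Delivery is then 25/32 = 78%, but 25/25 = 100% once the 7 others are filed under the two available reasons. The arithmetic is right, but the protocol defines no such denominator and plans no such analysis. Indirect information also exists: TNM stage crossed with not required, multidisciplinary discussion, frailty, day of death, and specialist team availability in the site survey. The supportable statement is that reasons for non-operation are not directly recorded.

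A second reply is that choosing the at-risk set belongs in an analysis plan, which is not shown. That is fair for M1, unresectable and R2 cases. It does not cover data that the form never collects.

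A third concerns the time origin. A reader might infer that sites count from different operations. The documents do not show this: follow-up starts on the day of the index surgery, and the protocol generally names revisional surgery when it means the second operation. Still, other fields name the index cholecystectomy or the repair explicitly, and this one says only surgery, so a clarifying word is worthwhile.

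Finally, with so few cancers across about 500 anticipated centres, reasons by country could hardly be estimated. That limits what the extra codes can show, but does not justify false ones.

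**Conclusion.** The point holds as a cheap improvement to data capture. Field 6 cannot record re-resection that was indicated but not done, so the reasons for non-operation are not directly measurable. The crude revision rate is sound. Field 8 cannot separate recurrence, persistent disease and absence of imaging, so crude recurrence may be biased in either direction and time to recurrence lacks a recorded disease-free censoring time.

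The documents do not support a fixed direction of bias. The sizes in the working rest on assumed cancer, non-operation, persistent-disease and recurrence shares; none comes from the protocol. The absence of the codes, and the fact that analysis can repair only part of the loss, do not depend on those assumptions.

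**What to change.** In Appendix A Section 5 and the Appendix B histology fields:

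- **Field 6:** keep the present options and add: No, indicated but not available; No, patient unfit; No, patient declined; No, died before surgery; No, pending at one year; Unknown.
- **Field 8:** add never disease-free and not imaged. If the answer is No, record days to last imaging.
- **Time origin:** state in field 8 and in the endpoint whether surgery means the index or the revisional operation.

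These are coding changes that follow the pattern of the preoperative imaging field. They leave patient management untouched. The cost is a few more response options and one number of days for malignant cases only, taken from the same notes with no extra visits. A margin field for the index specimen, or a clock starting at the last curative-intent operation, would be optional redesign and is not needed to meet this point.

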- **Return to theatre:** Each patient should only be entered into the study once. Any patient returning to theatre and requiring a cholecystectomy for whatever indication, should not be included.
- **Known gallbladder malignancy:** when the diagnosis of gallbladder cancer is established pre-operatively, the patient should be excluded. However, if gallbladder cancer is found unexpectedly during or after cholecystectomy (i.e. on histology), the patient should be included.

STUDY PROCEDURES

Site Survey

In order to describe local processes and resources, each site will be asked to complete an online site survey questionnaire to delineate the variation of cholecystectomy services and training amongst included hospitals (**Appendix C**).

*Completion of the short site survey can be done by a supervising consultant (preferred) or a hospital lead trainee that is familiar with the cholecystectomy practices at your site. Completion of the site survey is necessary before the site is granted access to the online **GECKO**: Data Collection form.*

Data Collection

Collaborators will collect data on consecutive eligible patient undergoing cholecystectomy within the pre-specified data collection periods (**Table 1; page 15**). Data collectors should use a combination of the **GECKO** Case Report Form (**Appendix A**) alongside the Data Dictionary (**Appendix B**) to successfully record required data on all eligible patients. Collaborators will create clear mechanisms appropriate to their institution to identify and include all eligible patients, involving daily review of operating logbooks, multidisciplinary team meeting, admission and handover lists. Local arrangements may include daily review of the patient and notes focused on included data points.

Data will be collected and stored online via the Research Electronic Data Capture (REDCap) web application (**see pages 20-21**), hosted and managed by the University of Edinburgh, United Kingdom. No patient identifiable data will be uploaded or stored on the REDCap database.

Strategies to identify consecutive eligible patients could include:

- *Daily review of elective theatre lists.*
- *Daily review of handover sheets/emergency admission and ward lists.*
- *Daily review of theatre logbooks (both elective and emergency).*

Follow-up Period

Centres will undertake patient follow-up at two timepoints:

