1. **30-day follow-up:** should be performed for all recruited patients. Each patient will be followed-up for 30 days starting on the day of surgery (day 0).
2. **One-year follow-up:** due to the nature of the study, aiming to assess bile duct injury and unsuspected gallbladder cancers, we aim to collect one-year follow-up data on all recruited patients. Each patient will be followed-up for one year starting on the day of surgery (day 0). Patients are excluded from one-year follow-up if they had died within 30 days of index surgery, as there would be no additional data to collect from these patients since the 30-day follow-up that had already been completed previously. Additional collaborators can be recruited to aid one-year follow-up data collection once the follow-up period begins (31st Jul 2024).

Local arrangements for successful 30-day and one-year follow-up may include: reviewing patient notes, reviewing patient status in outpatient clinics or via telephone interview at 30 days (if this is normal practice) and checking for readmission through handover lists. Follow-up should be performed in line with current routine practices of each hospital. No additional telephone, in-person or questionnaire-based follow-up is required. Source data may be acquired from hospital in-patient notes, clinical electronic systems, or outpatient letters.

Key to successful 1-year follow-up:

1. *Ensure you keep a list of all patient ID and corresponding RedCap ID in a safe, secure computer to allow follow-up of these patients. This will be in the form of an encrypted spreadsheet held securely on the local hospital computer network by a member of the data collection team (a hospital lead, supervising consultant/attending, or audit officer).*
2. *Where it is anticipated that a hospital lead will rotate to another hospital, then the supervising consultant should facilitate the secure storage of patient ID and corresponding RedCap ID.*
3. *Ensure the audit office / local governing bodies are clear this will be a follow-up study.*
4. *In high-volume centres where achieving high data completeness may be burdensome, involvement additional team members to provide support can be permitted.*

Table 1: Data collection periods

Dates	Description
00:00 31 st July – 23:59 13 th Aug 2023	Start of data collection period 1 (+ 30-day follow-up: ends 12 th Sep 2023) (+ one-year follow-up: ends 13 th Aug 2024)

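### The one-year form records death only as Clavien-Dindo grade V, so late deaths from cancer or unrelated causes either enter the complication rate or go unrecorded, depending on how a site reads the item

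*Protocol*

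**What the plan says.** - **One-year form.** Section 6 of the case report form (Appendix A) has the item "Highest one-year Clavien-Dindo (CD"), whose last option is "V (Postop day of death"). The matching entry in Appendix B, One-year Outcomes, item 1, says that for a death the site should "please indicate time from index cholecystectomy to death: number of days (whole number"). No other general item on the form records death.
- **Definition.** The Clavien-Dindo table in Appendix D defines grade V by the single word for death. It does not limit the grade to deaths caused by a complication.
- **Complication-level grades.** Item 3 of the one-year outcomes lists seven complications: surgical site infection, pulmonary complications, bile leak, biliary stricture, bleeding, intra-abdominal collection and acute pancreatitis. It instructs: "For all of the above, please indicate the Clavien-Dindo grade associated with that complication". Each can be graded up to V.
- **Who reaches this form.** Under Follow-up Period: "Patients are excluded from one-year follow-up if they had died within 30 days of index surgery". One-year grade V therefore covers only deaths after day 30.
- **Cancer patients.** Under Exclusion Criteria: "if gallbladder cancer is found unexpectedly during or after cholecystectomy (i.e. on histology), the patient should be included". Their last follow-up field is "Recurrence on imaging at one year", with days to recurrence.
- **Endpoints.** Under Secondary Outcome Measures, the 30-day and one-year outcomes of unsuspected gallbladder cancer begin with "1) complication rates (Clavien-Dindo classification"). The 30-day and one-year textbook outcome names graded complications and mortality as two separate components.

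**The concern.** One field has two jobs. It is the source for the one-year complication grade and the only general source for one-year death. The secondary endpoints treat these as different quantities.

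Deaths unconnected with surgery are foreseeable. The cohort keeps unsuspected gallbladder cancers, has no upper age limit, records ASA grades up to V and is followed for a year. With no cause item and no alternative place for a death, each site must decide what grade V means:

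- Under the literal reading, a death from tumour progression at eight months is a grade V complication.
- Under the surgical reading, the same patient receives the highest grade reached by a true complication, possibly 0, and the death is not recorded.

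The protocol anticipates around 500 centres and sets out to describe international variation. A difference in how sites read the item would appear in the results as a difference in outcome. The quantities at stake are the one-year complication rate, above all in unsuspected gallbladder cancer, and, where deaths go unrecorded, one-year mortality and the textbook outcome.

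**Working it through.** The plan states no figure on this point, so there is none to reproduce. The check has three parts.

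**1. Field count.** In Appendices A and B there are no fields for vital status separate from Clavien-Dindo, none for cause of death and none for relatedness. The one-year outcomes have one field for time to death and seven complication-level grades that can be set to V. None of the seven covers cancer progression, an unrelated cause or an unlisted complication. The only attributed death in the data dictionary is inside the stricture definition, which mentions death from liver failure and applies to surgically repaired bile duct injury.

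**2. What the form holds after a death between day 31 and one year.**

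| True cause | Site reads V as any death | Site reads the scale as surgical complications only |
|---|---|---|
| One of the seven listed complications | Highest grade V; that complication at V | Same |
| Unlisted complication | Highest grade V; no listed complication at V | Same |
| Gallbladder cancer | Highest grade V; no listed complication at V | Grade below V; death not recorded |
| Unrelated cause | Highest grade V; no listed complication at V | Grade below V; death not recorded |

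Only the first row can be attributed with confidence. In the second column the last three rows are identical. Malignant histology and recurrence are recorded, so deaths in cancer patients can be listed apart, but that does not show that the cancer caused the death. In the third column the last two rows look like survivors.

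**3. Direction and possible size.** Let c be the proportion with a true complication and m the proportion who die of a non-surgical cause after day 30. With every such death coded V, the recorded complication rate is the proportion with either event. It lies between max(c, m) and c + m (capped at 1), and under independence it is 1 − (1 − c)(1 − m). It can never fall below c, so the bias is upward or nil. With every such death left out, the recorded complication rate stays at c, but m is missing from mortality.

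The documents give neither c nor m. For illustration only, in cancer patients assume c = 0.15 and m from 0.20 to 0.40:

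- m = 0.20: independence gives 1 − 0.85 × 0.80 = 0.32; bounds 0.20 to 0.35.
- m = 0.40: independence gives 1 − 0.85 × 0.60 = 0.49; bounds 0.40 to 0.55.

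For the whole cohort, assume that 0.5% to 2% of the anticipated 15,000 die of any cause after day 30. Then 15,000 × 0.005 = 75 and 15,000 × 0.02 = 300 deaths could be coded V. This is an upper bound on misclassification under those assumed rates, because it includes any deaths that really were due to surgery.

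**The case against.** A reader might infer that the protocol makes sites score every unrelated death as a surgical complication. It does not. No section gives that instruction, the textbook outcome ties the scale to postoperative complications, and grade I is framed as a departure from an ordinary recovery. What the documents support is an ambiguity with two possible errors.

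A reader might also infer that one-year mortality cannot be estimated, or that the textbook outcome is necessarily wrong. That does not follow either. If all sites code every death as V, all-cause mortality is obtained by adding 30-day and later deaths. If the textbook outcome is all-or-none (an assumption, since the protocol does not say so) and counts all-cause death, a late death fails it through the mortality component whether or not it is also called a complication. The textbook outcome suffers only where deaths are left out. Failures are then undercounted and the rate looks too good.

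The analysis can also repair part of this. A statistical analysis plan, which is not at hand, could build the complication rate from the item 3 grades, or report separately the patients with highest grade V and no listed complication at V. That stands. But it cannot divide that group into cancer, unrelated cause and unlisted complication, and it cannot restore a death that was never entered. The Data Governance section also says the record ID, the only link to local patient lists, is stripped at anonymisation, so later queries could not be matched to patients.

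Finally, follow-up relies on routine notes and requires no extra contact, so omitting locally judged cause is a defensible economy. The primary endpoint, compliance with audit standards, does not use one-year death. Both points limit the weight of the concern without removing it.

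**Conclusion.** The point holds as a low-cost improvement to secondary endpoints. One item carries both the one-year complication grade and one-year death, with an unqualified definition of grade V and no cause. Depending on the site's reading, late deaths from cancer or unrelated causes either raise the one-year Clavien-Dindo complication rate or are lost from mortality and the textbook outcome. The effect is clearest in unsuspected gallbladder cancer. Item 3 limits the problem to deaths with no listed complication at V and deaths never entered.

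The direction under each reading needs no assumed rate. The size cannot be derived from the documents: the illustrative figures rest on assumed complication and death rates, and the single values of 0.32 and 0.49 also on independence. How many sites would choose each reading is unknown.

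**What to change.** Add three items to the one-year section of Appendices A and B:

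- vital status: alive, dead or not known;
- day of death;
- cause: complication of cholecystectomy or its treatment, gallbladder cancer, other, or unknown.

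Then state in the protocol or analysis plan that:

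- all-cause one-year mortality is taken from vital status, together with deaths already recorded by day 30;
- grade V counts in the one-year complication rate only when the death is attributed to a complication;
- deaths of unknown cause are shown separately or counted as complications in a sensitivity analysis;
- mortality remains a separate component of the textbook outcome.

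The cost is a few short fields, completed from notes that sites already review, on a form whose use the protocol dates from 31 July 2024, after recruitment closes on 19 November 2023. The items must be collected before record IDs are stripped. The drawback is that cause will be judged locally without adjudication and will be unknown for some patients.
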